## 1. BACKGROUND AND RATIONALE

Tacrolimus (FK) remains the cornerstone of maintenance immunosuppressants after renal transplantation. However, it is characterised by narrow therapeutic index and large inter-individual variability in its pharmacokinetics, particularly in the dose required to reach target trough blood concentrations. Among several factors investigated for their possible influence on tacrolimus pharmacokinetics, polymorphisms in genes coding for biotransformation enzymes (cytochrome P450 (CYP) isoenzymes 3A4 and 3A5) have received much attention. Exposure to FK correlates with the cytochrome P450 (CYP) 3A4 and CYP3A5 which are polymorphically expressed. This is in part explained by the presence of single-nucleotide polymorphisms (SNPs) in the CYP3A5 and CYP3A4 genes.

A SNP at position 6986 of the CYP3A5 gene (rs776746; 6986A>G; designated as CYP3A5 \*3) results in a splicing defect that causes non-functional CYP3A5 protein (Birdwell KA et al, 2015). In retrospective studies, it has been demonstrated that whole-blood tacrolimus trough concentration and tacrolimus dose requirements are closely associated with CYP3A5 polymorphism: patients carrying at least one CYP3A5\*1 allele have a lower tacrolimus concentration/dose ratio than that in nonexpressers (CYP3A5\*3/\*3) among kidney, liver, lung, and heart transplant recipients. In a cohort of kidney transplant recipients, a 2.3-fold difference was observed in the daily dose required to maintain target FK trough concentration in CYP3A5\*3\*3 and CYP3A5\*1\*1 patients (Haufroid V et al, 2004). Moreover, a significant delay in reaching target FK trough concentration and a shorter time to acute rejection were observed during the first 2 weeks after kidney transplantation in CYP3A5 expressers (MacPhee et al, 2004).

To date, renal transplant (RTx) recipients receive standard weight-based dosing of FK and therapeutic drug monitoring is employed for subsequent dose adjustment to ensure target FK concentration is attained. However, the current weight-based dosing strategies to guide the initial FK dosing have been poorly predictive of the actual FK dose required to attain therapeutic FK level (Loh PT et al, 2008). With the increased possibility of sub-therapeutic FK level during the early phase post renal transplantation, it puts them at a higher risk of developing acute rejection.

There has been increasing evidence to suggest the implementation of pre-transplantation genotyping to guide the initial FK dose to achieve target FK concentrations as quickly as possible (Chen SY et al, 2013; Shuker N et al, 2016; Pallen N et al, 2016; Zhang J et al. 2010). Min SI et al revealed that in RTx patients who received equal doses of FK, the CYP3A5 expressers (\*1\*1 and \*1\*3 genotypes) had lower FK level and a higher incidence of acute cellular mediated rejection than the CYP3A5 non-expressers (CYP35 \*3\*3 genotype). Furthermore, multivariate analysis identified CYP3A5 expression as an independent risk factor for cellular mediated rejection (odds ratio 2.79; p=0.043) (Min SI et al, 2010). On the contrary, there are a few studies that report contradictory results of genotype-guided FK dosing as being useful in attainment of target therapeutic levels. A randomized controlled trial by Thervet et al demonstrated that while target FK levels were achieved earlier in incident kidney transplant recipients whose tacrolimus dose was chosen based on CYP3A5 genotype versus a control group that started tacrolimus based on standard weight-based dosing (Thervet et al, 2010), no

differences were seen in patient survival, nephrotoxicity, or acute rejection over the three-month follow-up. A key limitation of the study was tacrolimus was introduced only 7 days after transplantation in the CYP3A5 genotype-based dosing group while it was started at time of transplantation in the weight-based dosing group. Prevalence of CYP3A5 genotypes is also different in various ethnicities. For example, the Caucasian proportions of CYP3A5 expressers (CYP3A5 \*1\*1 and \*1\*3) were 18% while in our local multiethnic population, CYP3A5 expressers make up 51% of the renal transplant population (Loh PT et al, 2008).

Given the differences in CYP3A5 genotype prevalence among races and the controversy in clinical benefits of such a pro-active dosage strategy, the impact of CYP3A5 genotype-guided dosing on clinical outcome remains to be answered, especially in the local multi-ethnic population. This pro-active approach may also sound promising for the local multi-ethnic population where majority of the renal transplant population are CYP3A5 expressers who may require a higher initial dose of FK based on genotyping profile (Loh PT et al, 2008). Faster achievement of target concentrations could potentially reduce the risk of graft rejection because of underexposure and toxicity because of overexposure (Birdwell KA et al, 2015). A recent meta-analysis including 21 studies evaluating the effect of CYP3A5 polymorphism on kidney transplant recipients concluded that there is a significantly increased risk for transplant rejection for those with the CYP3A5\*1\*1 or CYP3A5\*1\*3 genotype (P=0.04; odds ratio=1.32) (Rojas et al, 2015). Furthermore, patients with the CYP3A5\*3\*3 (nonexpresser) genotype exhibited dose-adjusted trough concentrations 1.8–2.5 times higher than CYP3A5 expressers during the first year after transplantation (Rojas et al, 2015).

This study aims to shed light on the possible impact of CYP3A genotype-based FK dosing on FK target achievement and clinical outcome after RTx in a multi-ethnic population where current evidence is lacking. This data would be helpful to the physicians so that by knowing the genotype of the patient before undergoing transplantation, they would be able to decide on the starting dose of FK so as to avoid low trough levels and risk of acute rejection or high trough levels and risk of nephrotoxicity.

## **2. HYPOTHESIS AND OBJECTIVES**

We hypothesise that the adaptation of CYP3A5 genotype-based FK dosing will lead to earlier FK target achievement and consequently, better clinical outcome after RTx.

This study aims to shed light on the possible impact of CYP3A genotype-based FK dosing on FK target achievement and clinical outcome after RTx in a multi-ethnic population where current evidence is lacking. This data would be helpful to the physicians so that by knowing the genotype of the patient before undergoing transplantation, they would be able to decide on the starting dose of FK so as to avoid low trough levels and risk of acute rejection or high trough levels and risk of nephrotoxicity.

## **3. EXPECTED RISKS AND BENEFITS**

The expected risks to the subjects include:

- Risks of venipuncture – Two additional blood tubes containing 3mls (1 teaspoon) of blood will be collected which will be timed with the other regular blood tests to minimize the discomfort of venipuncture

- Breach of patient confidentiality - Personal data will be collected and stored in a secured, password encrypted device which will only be accessed by the investigators to maintain patient confidentiality
- Risks of supra- or subtherapeutic tacrolimus levels - There could be potential risk associated with high tacrolimus dose/level (e.g. risk of high potassium, liver impairment, renal impairment) and low tacrolimus dose/level (e.g. risk of kidney rejection). This may potentially occur regardless of whether the subjects are dosed by genotyping or by standard weight-based dosing

The expected benefits to the subjects include:

- There is no assurance that the subject will directly benefit from this study. However, their participation may contribute to the medical knowledge about the potential use of identifying various CYP3A5 gene version to determine the initial dosing of tacrolimus in kidney transplant recipients

## **4. STUDY POPULATION**

### **4.1. List the number and nature of subjects to be enrolled.**

The number of living kidney donor transplants performed at Singapore General Hospital (SGH) is low - usually between 20 to 30 kidney transplants per year. Therefore, it is unrealistic to plan for a randomized controlled study as it will take years to achieve sufficient numbers for an adequately powered study. We aim for this study to be a pilot study to determine if there is any trend in correlation between CYP3A4 genotype and dosing. If there is any trend in correlation, we can then propose to design an adequately powered and likely multi-centre study to confirm any preliminary findings from this pilot study.

Thence it is decided that we will aim to recruit 100 subjects who are between the ages of 21 and 75 years old and are scheduled to receive renal transplant from a living donor and follow up at SGH between January 2021 to January 2023. The control group selected will be a historical cohort which had received tacrolimus based on weight-based dosing while the intervention group will be a prospective cohort.

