### **4.2. Criteria for Recruitment and Recruitment Process**

For the historical control group, all patients who have received living donor renal transplant between January 2016 to December 2020 at Singapore General Hospital and still currently on follow-up will be screened by the investigators to see if they meet the eligibility criteria and recruited if all criteria are met.

For the prospective group, all patients planned for a living donor renal transplant at Singapore General Hospital between January 2021 to January 2023 will be identified by the transplant coordinators and screened by the investigators to see if the subject meet the eligibility criteria and recruited if all criteria are met.

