### **4.3. Inclusion Criteria**

To be eligible for inclusion into the study, the subject should meet the following criteria:

- On follow up at SGH between the ages of 21 and 75 years old who had received or are

- scheduled to receive a living donor renal transplant between January 2016 to January 2023
- Has to receive tacrolimus (FK) (Prograf®; Astellas Pharma, Singapore), mycophenolic acid (MPA) (Cellcept®; Roche, Basel, Switzerland or Myfortic®; Novartis Pharma AG, Basel, Switzerland) and prednisolone as triple immunosuppressive drug maintenance regimen

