## **8. SAMPLE SIZE AND STATISTICAL METHODS**

### **8.1. Determination of Sample Size**

The number of living kidney donor transplants performed at Singapore General Hospital (SGH) is low - usually between 10 to 20 kidney transplants per year. Therefore, it is unrealistic to plan for a randomized controlled study as it will take years to achieve sufficient numbers for an adequately powered study. We aim for this study to be a pilot study to determine if there is any trend in correlation between CYP3A4 genotype and dosing. If there is any trend in correlation, we can then propose to design an adequately powered and likely multi-centre study to confirm any preliminary findings from this pilot study

Thence, upon consultation with the biostatistician, it is decided that we will recruit 100 subjects who are between the ages of 21 and 75 years old and are scheduled to receive renal transplant

from a living donor and follow up at SGH between January 2016 to January 2023. The control group selected will be a historical cohort which had received tacrolimus based on weight-based dosing while the intervention group will be a prospective cohort.

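### Sections 4.1 and 8.1 give the same 100-subject target two accrual rates and two windows; read literally, section 4.1's target cannot be met at either rate

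*Protocol*

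**What the plan says.** Sections 4.1 and 8.1 contain nearly the same paragraph. Each gives the centre's living-donor transplant volume, argues from it that a randomised trial is unrealistic, and sets a target of 100 subjects. Two facts differ.

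- **Rate.** Section 4.1: "usually between 20 to 30 kidney transplants per year". Section 8.1: "usually between 10 to 20 kidney transplants per year".
- **Window for the 100.** Section 4.1: "we will aim to recruit 100 subjects who are between the ages of 21 and 75 years old and are scheduled to receive renal" transplants "from a living donor and follow up at SGH between January 2021 to January 2023". Section 8.1: "from a living donor and follow up at SGH between January 2016 to January 2023".

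Both paragraphs end by naming a historical control cohort and a prospective intervention cohort. Section 4.2 dates the two. The historical group is "all patients who have received living donor renal transplant between January 2016 to December 2020 at Singapore General Hospital and still currently on follow-up"; the prospective group is "all patients planned for a living donor renal transplant at Singapore General Hospital between January 2021 to January 2023". The section 4.3 inclusion criterion spans both periods, covering patients already transplanted or "scheduled to receive a living donor renal transplant between January 2016 to January 2023". No section divides the 100 between the cohorts.

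**The concern.** Both paragraphs describe the same centre, the same type of transplant and the same target, so at most one version of each figure can be right. The two rate ranges meet only at 20 a year, and the windows start five years apart.

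Section 4.1, as worded, attaches all 100 subjects to the prospective period alone, where neither stated rate comes near 100. Section 8.1 uses the long window but still describes all 100 as awaiting transplant, although most of that window had passed before the prospective arm opened. Neither is a clean statement of a combined total.

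What is at stake is the size of the prospective arm, the only one that receives genotype-based dosing. A reader or the ethics board cannot tell whether to expect about 20 patients, about 60, or 100. The rate also carries the protocol's stated reason for not randomising, so it should not appear in two versions.

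**Working it through.** The protocol derives the 100 from no power calculation; section 8.1 says only that it was decided after consulting the biostatistician. The available check is accrual.

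**Inputs**

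- Target: 100 (sections 4.1 and 8.1).
- Rates: 20–30 a year (section 4.1); 10–20 a year (section 8.1).
- Prospective window: January 2021 to January 2023, 24 or 25 months depending on whether the last January counts (sections 4.1 and 4.2). The grant period in section 14, 4 January 2021 to 3 January 2023, fits 24 months.
- Historical window: January 2016 to December 2020, 60 months (section 4.2).
- Combined window: January 2016 to January 2023, 84 or 85 months (sections 4.3 and 8.1).

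**Formula**

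Maximum patients = annual rate × months / 12, assuming every transplanted patient is eligible and enrolled. Fractions are rounded down in the text.

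| Period | At 20–30 a year | At 10–20 a year |
|---|---|---|
| Prospective, 24–25 months | 20 × 24/12 = 40 to 30 × 25/12 = 62.5 | 10 × 24/12 = 20 to 20 × 25/12 = 41.7 |
| Historical, 60 months | 20 × 5 = 100 to 30 × 5 = 150 | 10 × 5 = 50 to 20 × 5 = 100 |
| Combined, 84–85 months | 20 × 84/12 = 140 to 30 × 85/12 = 212.5 | 10 × 84/12 = 70 to 20 × 85/12 = 141.7 |

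**Literal reading of section 4.1 (100 in the prospective window)**

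The stated 100 is not reproduced. The most the window gives is 62 at section 4.1's own rate and 41 at section 8.1's. Reaching 100 would need 100 × 12/25 = 48 to 100 × 12/24 = 50 transplants a year.

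**Combined reading (100 across both cohorts)**

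- Rate needed with no losses: 100 × 12/85 = 14.1 to 100 × 12/84 = 14.3 a year. The lower part of section 8.1's range falls short.
- Share that must be eligible and enrolled at section 8.1's rate: at 20 a year, 100/141.7 = 70.6% to 100/140 = 71.4%; at 15 a year, 100/106.25 = 94.1% to 100/105 = 95.2%.
- Share at section 4.1's rate: 100/212.5 = 47.1% to 100/140 = 71.4%. Since section 4.2 takes every eligible patient, the total passes 100 unless 28.6% to 52.9% are lost to ineligibility, refusal or, for historical patients, no longer being followed at the centre.

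**The case against.** The strongest reply is that 100 plainly means both cohorts together. Section 4.1's next sentence names the historical group, sections 4.3 and 8.1 use 2016 to 2023, and section 4.2 dates each cohort clearly. On that view the 2021 start in section 4.1 is a drafting slip, and showing that it is infeasible refutes a reading nobody intended. This is probably right about intent. It leaves the conflicting rates untouched, and the combined total is still not stated anywhere.

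A second reply is that little depends on the figure. The study is a pilot, the case against randomising is the same at 10–20 or 20–30 a year, the section 6.3 stopping rule is a percentage, and no test, endpoint or eligibility rule uses the rate. That stands, and it limits the point to planning and ethical review rather than the validity of the analysis.

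Third, 100 is worded as an aim, so exceeding it breaks no rule, and the documents give no loss rates. That also stands. The overshoot figures show only that the two rates describe different studies. Finally, both rates are given as usual ranges, so the maxima above are not absolute. Even so, the 48 to 50 a year that section 4.1 would need lies far outside either range.

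**Conclusion.** The concern holds. Sections 4.1 and 8.1 contradict each other on both the accrual rate and the window for one target, and section 4.1's target as worded is out of reach at either rate. The prospective arm can be at most about 40–62 patients if section 4.1's rate is right and about 20–41 if section 8.1's is; in neither case is it 100. As a total over both cohorts, 100 is attainable, but at 10–20 a year it needs an average of about 14 a year with no losses, while at 20–30 a year it may well be exceeded.

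These figures assume that the usual ranges hold throughout and that nobody is excluded or refuses, so realistic numbers are lower. Which rate is right cannot be settled from the protocol. This should be fixed, but it does not undermine the planned comparisons.

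**What to change.** - Take one annual rate from the centre's transplant log and state it, with one window, in both sections 4.1 and 8.1.
- Say that 100 is the total of the historical and prospective cohorts, if that is the intent; otherwise restate the target.
- Reword section 8.1 so that patients already transplanted are not described as awaiting transplant.
- Give the expected number in each cohort: the agreed rate times 5 years for the historical group and 24 or 25 months for the prospective group (fixing which), reduced for exclusions, refusals and the requirement that historical patients remain under follow-up.
- State the prospective arm as what 2021 to 2023 can deliver, no more than about 62 even at the highest stated rate.

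This is a text amendment. It needs no extra patients and changes no procedure, endpoint or test. Its only drawback is that the stated size, above all of the prospective arm, will look less favourable.

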### **4.2. Criteria for Recruitment and Recruitment Process**

For the historical control group, all patients who have received living donor renal transplant between January 2016 to December 2020 at Singapore General Hospital and still currently on follow-up will be screened by the investigators to see if they meet the eligibility criteria and recruited if all criteria are met.

For the prospective group, all patients planned for a living donor renal transplant at Singapore General Hospital between January 2021 to January 2023 will be identified by the transplant coordinators and screened by the investigators to see if the subject meet the eligibility criteria and recruited if all criteria are met.

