#### Endpoints

The primary endpoint of the study is the proportion of patients within the desired FK trough level at first steady state e.g. morning of day 3 after five unaltered FK doses and the proportion of patients within target FK levels on day 7 post initiation of FK. The FK trough level is defined as the whole blood concentration 12 h  $\pm$  15 min after the previous dose taken the night before at 8pm. Thereafter, the clinicians can change the FK dose based on the measured FK

level and/or the clinical situation of the individual patient according to routine transplant immunosuppression protocol. For the genotyping arm, the pre-specified FK target range will be 10 – 15 ng/mL in the first 1 week after transplantation and subsequently adjusted based on routine transplant immunosuppression protocol.

Secondary pharmacokinetic endpoints include

- Proportion of patients within target FK levels on day 7 post renal transplant
- Average FK level during the first 1 weeks after transplantation
- Average daily dose of FK the first 90 days post transplantation [days 3, 7, 14±3, 30±3, 60±3, 90±3 days post transplantation]
- Average concentration-to-dose ratio of FK during the first 90 days post transplantation [days 3, 7, 14±3, 30±3, 60±3, 90±3 days post transplantation]
- Time to reach the first target FK range
- Number of FK dose adjustments required to reach the target FK level
- Number of markedly sub-therapeutic FK level (defined as <4 ng/mL) and markedly supra-therapeutic FK level (defined as > 20 ng/mL)

Secondary clinical endpoints include

- Incidence of biopsy-proven acute rejection (BPAR), with histologic characteristics described accordingly to the Banff criteria [Banff 1997 scoring system with 2007 modifications] and/or clinically presumed acute rejection
- Incidence of graft loss (defined as failure to discontinue dialysis or if patient undergoes graft nephrectomy)
- Renal function at month 3 after transplantation. Estimated GFR (eGFR) will be calculated using CKDEPI equation. [Time Frame: at day 7, 14, 30±3, 60±3 and 90±3 days after transplantation ]

All patients will be followed for at least 3 months after transplantation, or until graft loss occurs (defined as death with a functioning transplant, return to dialysis or re-transplantation), whichever occurs earlier.

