#### FK measurement and genotyping

FK trough level will be determined in whole blood using liquid chromatography and tandem mass spectrometry (LC-MS/MS) method.

Two venous blood samples (3 mL each) for CYP3A5 genotyping will be obtained from all study participants. The subjects' blood samples will be de-identified and sent to the molecular laboratory in Tan Tock Seng Hospital, Singapore, which is offering CYP3A5 genotyping as a clinical service. Briefly, the genomic DNA is extracted from ethylenediaminetetraacetic acid anticoagulated whole blood samples using a QIAamp DNA mini kit (Qiagen, Hilden,

Germany), according to the manufacturer's protocol. Real-time polymerase chain reaction (RT-PCR) is then performed with a 7900 Real-Time PCR System. RT-PCR consisted of a denaturation step at 95°C for 10 minutes, then 50 cycles of 15 seconds at 92°C and 1 minute 30 seconds at 69°C. CYP3A5 6986A>G (rs776746) allelic discrimination is undertaken with a Custom TaqMan® SNP Genotyping Assay and VIC and FAM reporter dyes. No phenotyping will be done for CYP3A5. Once the blood sample has been genotyped, it will be destroyed as agreed upon by the molecular laboratory at Tan Tock Seng Hospital. The genotyping results will then be re-identified by the PI or co-investigators. The genotyping result will not be communicated to the subjects.

The blood sample will be destroyed immediately after sample analysis.

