## **8.2. Statistical and Analytical Plans**

For the analysis of efficacy, the intention-to-treat analysis will be used, which will include all patients who were treated with at least one dose of FK. Categorical variables are reported using frequency and percentages while continuous variables are expressed as medians with ranges. A chi-square statistic will be used to evaluate the null hypothesis of no difference between the standard dose group and genotype based group within the FK target range on day 3 after transplantation. Continuous data will be compared using the Mann-Whitney U test. The time to reach target FK range will be estimated with Kaplan-Meier survival analysis and compared between the groups using log-rank test. To estimate the overall effect of CYP3A5 genotype on the outcome variables of FK daily dose, FK trough concentration and dose-adjusted FK level (a measure of apparent oral clearance), a mixed between-within subjects analysis of variance will be used. This analysis will also be used to estimate the overall effect of dosing approach on renal function. All data are analysed using R Core Team (2017). A p-value < 0.05 is considered statistically significant.

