### **11.1. Informed Consent**

Participants will be approached during their routine clinic visit before transplant ethic

committee by the investigators to participate in the study and the informed consent will be taken in the presence of a witness. The consent process will take place in a consultation room in the clinic to ensure privacy and allow the investigator to explain the nature of the study to the participants. The consent process informs the participant about the study, indicates the participation is voluntary and he/she has the right to stop at any time. Risks are enumerated in the informed consent form and described orally during the consent process. The consent will be communicated in a language that is understood by the prospective participant or the legal representative. Participants will be given ample time during the clinic visit to consider participation in study. If the potential research participant does not speak or understand English, a translator will be engaged to help in the consent taking process and will act as witness for the informed consent. Copies of the current, IRB-approved consent form detailing the risks and benefits of study participation will be provided to the participants.

In obtaining and documenting informed consent, the investigator will comply with the GCP guidelines and to the ethical principles that have their origin in the Declaration of Helsinki.

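### Historical controls must still be on follow-up when screened and genotype-arm patients need not be, so control deaths drop out and the comparison of clinical and safety outcomes is not like with like

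*Protocol*

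**What the plan says.** **Entry of controls (Protocol 4.2).** Candidates are living-donor recipients transplanted between January 2016 and December 2020, and of these it is patients "at Singapore General Hospital and still currently on follow-up will be screened by the investigators to see if they meet the eligibility criteria".

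**Entry of the genotype arm (Protocol 4.2).** Here "all patients planned for a living donor renal transplant at Singapore General Hospital between January 2021 to January 2023 will be identified"; the coordinators do this and the investigators then screen them. Nothing is required of them after transplant.

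**Common criterion (Protocol 4.3).** The first inclusion criterion begins "On follow up at SGH between the ages of 21 and 75 years old who had received or are" and covers both cohorts.

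**Genotyping (Protocol 5, FK measurement and genotyping).** Blood "for CYP3A5 genotyping will be obtained from all study participants".

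**Consent (Protocol 11.1).** The only route described is before transplant: "Participants will be approached during their routine clinic visit before transplant ethic" committee review.

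**Analysis set (Protocol 8.2).** The efficacy analysis is called intention-to-treat, "which will include all patients who were treated with at least one dose of FK".

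**Outcomes concerned.** Section 5 lists rejection and graft loss as secondary clinical endpoints and death among the serious adverse events. Patients are followed for at least 3 months, and sections 5 and 7.2 limit data retrieval to 3 months after transplant.

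**The concern.** The status that admits a control is observed after the outcome has happened. If screening starts in January 2021, it comes up to about five years after transplant, and for nearly all controls the 3-month window has already closed. Genotype-arm patients enter before the window opens, so their early deaths and losses are counted. This is survivor selection in one cohort only.

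The follow-up criterion in 4.3 does not even this out. A prospective patient can meet it before transplant, whereas a control meets it only afterwards. The genotyping sample adds to the problem, since a deceased control cannot give one. The analysis set in 8.2 cannot repair it either: a treated control who was never admitted is not there to be analysed.

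Section 2 hypothesises better clinical outcome with genotype-based dosing, and sections 4.1 and 8.1 say that trends from this pilot would lead to a larger study. A distorted clinical or safety contrast would be carried forward. For death the distortion runs against genotype-based dosing.

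**Working it through.** The protocol gives no event rate, retention rate or split of its 100 subjects between cohorts, so there is no figure to reproduce. The entry rule is settled by reading the text; the sizes below are illustrations on stated assumptions.

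**1. What follows from the text alone**

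| Event before screening | Control | Genotype arm |
|---|---|---|
| Death | cannot enter | enters and is counted |
| Graft loss or rejection, still on follow-up | enters and is counted | enters and is counted |
| Graft loss or rejection, left follow-up | cannot enter | enters and is counted |

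The first row is certain. The third depends on who left follow-up, which the protocol does not say. The exception to the first row is a late-2020 control whose day 90 falls after screening.

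**2. Control deaths removed.** Expected number = n × p; chance of at least one = 1 − (1 − p)^n. Assumed: n = 50 or 70 controls, p = 3-month death risk.

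| p | n = 50: expected | n = 50: at least one | n = 70: expected | n = 70: at least one |
|---|---|---|---|---|
| 1% | 0.5 | 40% | 0.7 | 51% |
| 2% | 1.0 | 64% | 1.4 | 76% |
| 5% | 2.5 | 92% | 3.5 | 97% |

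Observed control mortality is 0 in every row.

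**3. How often the imbalance would be visible.** Two years at 10 to 20 transplants a year (section 8.1) or 20 to 30 (section 4.1) gives 20 to 60 genotype-arm patients. By the same formula, the chance of at least one genotype-arm death is 18%, 33% or 45% for 20, 40 or 60 patients at p = 1%, and 33%, 55% or 70% at p = 2%. This is not the size of the bias. It is the chance that a death in one arm is set against a zero that the entry rule created.

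**4. Rejection.** Assume a true risk of 15% in both cohorts, 90% of non-rejectors retained, and a share r of rejectors retained. Observed control risk = 0.15r / (0.15r + 0.85 × 0.90). The spurious risk ratio (genotype arm over control) is 0.15 divided by that.

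| r | Observed control risk | Risk ratio |
|---|---|---|
| 70% | 12.1% | 1.24 |
| 80% | 13.6% | 1.11 |
| 90% | 15.0% | 1.00 |
| 95% | 15.7% | 0.96 |

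**5. Graft loss.** Same form, with an assumed true risk of 2%: observed = 0.02r / (0.02r + 0.98 × 0.90).

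| r | Observed control risk | Risk ratio |
|---|---|---|
| 50% | 1.12% | 1.78 |
| 75% | 1.67% | 1.20 |
| 90% | 2.00% | 1.00 |
| 100% | 2.22% | 0.90 |

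**6. Primary endpoint.** Trough at a given dose depends on genotype, so the question is whether selection shifts the controls' genotype mix. Inputs from section 1: 51% expressers, and odds ratios for rejection of 1.32 and 2.79. Assumed: 15% rejection overall, with 70% of rejectors and 90% of others retained. Retention in a genotype group = 0.90 − 0.20 × its rejection risk.

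- Odds ratio 1.32: risks 16.7% and 13.2%, retention 0.867 and 0.874. Expresser share = 0.51 × 0.867 / (0.51 × 0.867 + 0.49 × 0.874) = 50.8%.
- Odds ratio 2.79: risks 21.0% and 8.7%, retention 0.858 and 0.883. Share = 50.3%.

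Against 51%, the shift is negligible.

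**The case against.** The strongest reply is that only the exclusion of deaths is established. For rejection and graft loss the direction is unknown, as steps 4 and 5 show: patients with complications may well be kept on follow-up more closely than others. The expected number of control deaths removed is about one at a risk of 1% to 2%, and no significance test would be swayed by it. With an assumed 40 genotype-arm patients and 50 controls, Fisher's two-sided p is 0.44 for 1 death against 0, 0.19 for 2 against 0 and 0.08 for 3 against 0. Section 8.2 names no test for these outcomes, and the study is a pilot. In the one outcome where bias is certain it works against genotyping, so it cannot manufacture a benefit there. Present contact also has a use, because 8.2 models the effect of genotype on dose and trough and that needs a sample.

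Most of this stands as a limit on size. Month-3 eGFR can also be left aside: in either cohort it is measured only in patients who reach month 3, so early deaths do not distort it in one arm only. What does not stand is the inference that the rule is harmless. Section 5 describes the study as a comparison of selected endpoints between the two cohorts, and a zero fixed by the entry rule is misleading whether or not it is tested. The genotype model loses nothing from the remedy, since the added controls would not have been enrolled under the present rule (provided the target of 100 is not used as a cap that lets them displace others).

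**Conclusion.** The concern holds. As written, the control entry rule excludes every control who died before screening, while genotype-arm deaths are counted. For controls past day 90 at screening, 3-month mortality is zero whatever the truth. Assuming 50 to 70 controls and a death risk of 1% to 5%, that removes 0.5 to 3.5 expected deaths. Bias in rejection and graft loss is possible but not established. It is absent if event patients are retained as often as others, runs against genotyping if they are retained less, and reverses if they are retained more. All event and retention rates here are assumed.

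The fault is confined to secondary clinical and safety outcomes, and the day-3 and day-7 trough comparison is little affected. It should be fixed because no later analysis can recover patients who were never admitted, and because the condition is not needed to measure any between-cohort outcome to 3 months. The fix does not remove the other weaknesses of a historical control.

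**What to change.** - **Section 4.2:** remove the current-follow-up condition. Define the controls as all consecutive living-donor recipients from January 2016 to December 2020 who met the criteria at the time of transplant, whatever their present status.
- **Section 4.3:** state that being on follow-up at the hospital is judged at the time of transplant in both cohorts.
- **Section 5, FK measurement and genotyping:** state that a control without a sample stays in the between-cohort comparison with genotype missing, and report how many there are.
- **Section 11.1:** add the consent route for controls, with a request to waive consent for record data to day 90 where it cannot be obtained.
- **If no waiver is granted:** report death, graft loss and rejection for the genotype arm without a between-cohort comparison.

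One related, minor point: section 5 defines the endpoint as "Incidence of graft loss (defined as failure to discontinue dialysis or if patient undergoes graft nephrectomy"), while its end-of-follow-up rule counts death with a functioning transplant as graft loss. Under the second wording the excluded control deaths would also be excluded graft losses. The two should be reconciled and one endpoint definition applied to both cohorts.

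The cost is a waiver request, some extra chart review limited to day 90, and some controls without a genotype, which the comparison of dosing approaches does not need.
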